**Table 1 Treatment adjustments for infusion response symptoms caused by AK**

104	
NCI-CTCAE grade	Regarding the treatment adjustment for AK 104
Level 1 mild Minor, temporary reaction; no infusion	Reduce the AK 104 infusion rate by 50% and closely monitor any deterioration. The total infusion time of AK 104 should not

interruption; no treatment.	exceed 120 minutes.

Level 2 moderate
 
Treatment or infusion interruption is required, but symptomatic treatment (such as antihistamines, NSAID, corticosteroids, intravenous infusion), rapid effect; preventive administration of <24 hours.
	
Interrupt the AK104 infusion.
 
The infusion was restarted at 50% of the previous infusion rate at times when the infusion response had subsided or the severity had dropped to at least level 1, and any deterioration was monitored closely.
 
If the subject has a second level 2 infusion reaction at a slower infusion rate, the infusion should be discontinued and the subject must be withdrawn from AK 104 treatment.

Grade 3 or 4 is serious or life-threatening
 
Grade 3: delay in symptom relief (e. g. symptomatic treatment and / or infusion interruption, lack of rapid response); relapse after symptom improvement; sequelae requiring hospitalization.
 
Grade 4: life-threatening; requiring urgent treatment.
	
The AK 104 infusion was stopped immediately, and the subject's infusion tube was disconnected.
 
Subjects must immediately withdraw from AK 104 treatment and must not receive any further AK 104 treatment.

### 8.3 Complications of infection

Bacterial, mold, tuberculosis virus infection and some special microorganisms of each system.

Countermeasures: Most of the above situations can be alleviated by themselves or improved after symptomatic treatment, and in rare cases, they may be life-threatening; the prevention measures include eliminating contraindications, strictly following the treatment procedures and specifications, strictly monitoring the subjects, and treating the symptoms according to the doctor.

#### 8.4 Immune-related adverse events (irAE)

The irAE is defined as an AE associated with drug exposure, consistent with an immune-mediated mechanism of action, and without a clear alternative etiology.

Based on the mechanism of action of AK 104 targeting PD-1 and CTLA-4 leading to T cell activation and proliferation, it is possible that irAE could be observed during the conduct of this study. The underlying irAE may be similar to the adverse events seen with anti-PD-1 / L1 drugs, including immune-mediated colitis, dermatitis, pneumonia, hepatitis, encephalitis, nephritis, and endocrine disorders. Subjects should be monitored for the signs and symptoms of an irAE. In the absence of other alternative causes (e. g., infection or PD), immune-related causes associated with signs or symptoms of colitis, dermatitis, pneumonia, hepatitis, encephalitis, nephritis, and endocrine disorders should be considered.

Based on the severity of toxicity occurring in treatment according to NCI CTCAE 5.0 grade, AK 104 treatment adjustments will be performed to manage potential irAEs.

- The maximum interval allowing an AK 104 pause is 12 weeks. If they could not return to the reuse of AK 104 within 12 weeks, the subject permanently discontinued AK 104 and entered the follow-up phase. Except: AK 104 was suspended for more than 12 weeks or AK 104 for more than 12 weeks due to AEs that may be unrelated or unrelated to AK 104. In this case, a discussion with the medical monitor is needed to decide whether the AK 104 treatment can be continued.

Generally, it is recommended to manage irAEs according to the following principles. Subjects should be comprehensively evaluated, excluding any other alternative etiology (e. g. disease progression, concomitant medication, infection, etc.). Serological, immunological, and histological (biopsy) data should be used to support the diagnosis of irAE, as appropriate.

- If applicable, systemic corticosteroids (e. g., prednisone or intravenous equivalent) should be considered for persistent low-grade or severe (grade 3) events.

- If symptoms recur or worsen during the glucocorticoid reduction, the dose was increased until the symptoms stabilized or improved, and then gradually rereduced at a slower rate.
- For events that do not respond to systemic corticosteroids, more potent immunosuppressive agents (e. g. infliximab, maccohenyl esters, etc.) should be considered after discussion with the medical monitor.
- Termination of study drug treatment is not mandatory for grade 3 or 4 inflammatory reactions (e. g., sites of metastatic disease, lymph nodes).
- Doctors in other fields (such as cardiology or autoimmune diseases) should be arranged to make appropriate treatment decisions.
- For multiple low-grade AEs (no treatment termination is required separately), AK 104 will be terminated at the discretion.
- After discontinuation of study drug for Grade 3 or 4 events, if the subject responded well and the toxicity resolved rapidly, AK 104 could be resumed after discussion with the medical monitor.
- For abnormal laboratory findings, suspension or permanent termination should be determined based on concomitant clinical symptoms / signs and the clinical judgment of the investigator.

AK 104 dose adjustment and toxicity management principles for immune-related AEs are shown in the following table for irAEs or when specific toxicities exist, refer to the management of immune-related adverse events in patients treated with immune checkpoint inhibitors: Clinical Practice Guidelines of the American Society for Clinical Oncology (Brahmer et al., 2018) processing. Guidelines for the diagnostic assessment of immune-related adverse events are detailed in the appendix.

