## **1.4 Risk / benefit assessment (must)**

### **1.4.1 Known potential risks**

The irAE is defined as an AE associated with drug exposure, consistent with an immune-mediated mechanism of action, and without a clear alternative etiology. Based on the mechanism of action of AK 104 targeting PD-1 and CTLA-4 leading to T cell activation and proliferation, it is possible that irAE could be observed during the conduct of this study. The underlying irAE may be similar to the adverse events

seen with anti-PD-1 / L1 drugs, including immune-mediated colitis, dermatitis, pneumonia, hepatitis, encephalitis, nephritis, and endocrine disorders.

Based on the severity of toxicity occurring in treatment according to NCI CTCAE 5.0 grade, AK 104 treatment adjustments will be performed to manage potential irAEs.

- The maximum interval allowing an AK 104 pause is 12 weeks. If not returning to AK 104 within 12 weeks, the subject permanently discontinued AK 104 and, if applicable, considered systemic corticosteroids (such as prednisone or intravenous equivalent) for persistent low grade or severe (grade 3) events.
- If symptoms recur or worsen during the glucocorticoid reduction, the dose was increased until the symptoms stabilized or improved, and then gradually rereduced at a slower rate.
- For events that do not respond to systemic corticosteroids, more potent immunosuppressive agents (e. g. infliximab, maccohenyl esters, etc.) should be considered after discussion with the medical monitor.
- For multiple low-grade AEs (no treatment termination is required separately), AK 104 will be terminated at the discretion.
- After discontinuation of study drug for Grade 3 or 4 events, if the subject responded well and the toxicity resolved rapidly, AK 104 could be resumed after discussion with the medical monitor.
- For abnormal laboratory findings, suspension or permanent termination should be determined based on concomitant clinical symptoms / signs and the clinical judgment of the investigator.

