**Table 2: The recommended principles for dose adjustment and toxicity management of AK 104 immune-related AEs**

Immune-related AEs	Toxicity level	Measures taken against AK 104	Management of irAE (corticosteroids and other treatments)	Monitoring and follow-up

pneumonia	Level 2	Suspension of medication	Corticosteroid hormone (initial dose of 1-2mg / kg prednisone or equivalent), then tapered thereafter	The subject was monitored for the symptoms and signs of pneumonia. Subjects with suspected pneumonia by imaging evaluation and were started on corticosteroid hormone therapy. Prophylactic use of antibiotics to prevent opportunistic infections
	Grade 3 – 4, or recurrent grade 2	Permanent withdrawal of drugs		
Diarrhea / enteritis	Level 2-3	Suspension of medication	Corticosteroid hormone (initial dose of 1-2mg / kg prednisone or equivalent), then tapered thereafter	Participants were monitored for symptoms and signs of gastroenteritis (diarrhea, abdominal pain, hematology, blood, stool, with or without fever) or bowel perforation (peritoneal irritation or intestinal obstruction). Subjects with grade 2 diarrhea and suspected enteritis should consider consulting a gastroenterologist for endoscopy to exclude enteritis
	Level 4	Permanent withdrawal of drugs		
AST/ALT	Level 2	Suspension of	Corticosteroid (initial	Monitor liver

Elevated or with an elevated bilirubin		medication	dose 0.5-1mg / kg prednisone or equivalent), tapered	function (weekly or more frequently until liver enzymes return to baseline or remain stable)
	Level 3	Suspend or permanently	Corticosteroid hormone (initial dose of 1-2mg / kg prednisone or equivalent), then tapered thereafter	
	Level 4	Permanent withdrawal of drugs	Corticosteroid hormone (initial dose of 1-2mg / kg prednisone or equivalent), then tapered thereafter	
Type 1 diabetes mellitus (T1DM) or hyperglycemia	New T1DM or hyperglycemia (related to cell failure)	Suspension of medication	T1DM subjects were started on insulin replacement therapy and hyperglycemic subjects were started on antidiabetic agents	The subject was monitored for blood glucose, or other symptoms and signs of diabetes
hypophysitis	Level 2	Suspension of medication	Use of corticosteroid hormones and, if clinically indicated, initiate hormone replacement therapy	Monitor for symptoms and signs of hypophysitis (including pituitary and adrenal dysfunction)
	Level 3-4	Suspend or permanently		

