hyperthyreia	Level 2	cont.rem	Treatment with nonselective receptor blockers (e. g. propranolol) or thioamide (if appropriate)	Monitor for the symptoms and signs of thyroid disease
	Level 3-4	Suspend or permanently		
hypothyreia	Level 2-4	cont.rem	Thyroid hormone replacement therapy was initiated based on standard therapy (e. g. L Thyroxine or triiodothyronine)	Monitor for the symptoms and signs of thyroid disease

Nephritis and renal insufficiency	Level 2	Suspension of medication	Corticosteroid hormone (initial dose of 1-2mg / kg prednisone or equivalent), then tapered thereafter	Monitor for changes in renal function
	Level 3-4	Permanent withdrawal of drugs		
carditis	Level 1	Suspension of medication	Corticosteroid hormones were used based on the type and severity of the AE	Ensure adequate evaluation to confirm the cause and or to exclude other causes
	Level 2	Suspend or permanently		
	Level 3-4	Permanent withdrawal of drugs		
All of the other irAEs	Level 2, that could not be tolerated or persisted	Suspension of medication	Corticosteroid hormones were used based on the type and severity of the AE	Ensure adequate evaluation to confirm the cause and or to exclude other causes
	Level 3	AEs based on type of AE suspension or permanent withdrawal include but are not limited to Guillain-Barre syndrome, encephalitis, etc		
	Grade 4 or recurrent grade 3	Permanent withdrawal of drugs		
1. Suspension or permanent withdrawal will be decided after discussion between the investigator and the medical supervisor pay attention to:				

When the AE returns to grade 0-1 or baseline, corticosteroid hormones began to be gradually reduced for more than 4 weeks;

For AK 104 suspension: restart AK 104 if the AE returns to Grade 0-1 or baseline with corticosteroid tapering (10mg prednisone or equivalent dose) and if the AE does not resolve within 12 weeks after the last dose or 12 weeks;

For severe and life-threatening irAEs, intravenous corticosteroids and sequential oral hormone therapy should be started, and if corticosteroids are not effective, other immunosuppressants should be considered;

For subjects with grade 3-4 immune-related endocrine disorders requiring AK 104 suspension, allow medication to resume when the AE returns to level 2 and is controlled by hormone replacement therapy or achieves metabolic stability (e. g., T1DM).

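### The bullet allowing AK 104 to be resumed after grade 3 or 4 events does not exclude the immune-related events for which Table 2 lists only permanent withdrawal

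*Protocol*

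**What the plan says.** Section 8.4 opens its list of management bullets with "Generally, it is recommended to manage irAEs according to the following principles". One bullet says that after the study drug has been discontinued "for Grade 3 or 4 events, if the subject responded well and the toxicity resolved rapidly, AK 104 could be resumed"; the condition that completes it is discussion with the medical monitor. Section 1.4.1 carries the same bullet, ending "AK 104 could be resumed after discussion with the medical monitor". Neither place names a toxicity to which it does not apply.

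After the bullets, 8.4 points to Table 2: "AK 104 dose adjustment and toxicity management principles for immune-related AEs are shown in the following table". The table's title is "The recommended principles for dose adjustment and toxicity management of AK 104 immune-related AEs". For several toxicities and grades the only action in the table is "Permanent withdrawal of drugs". In the catch-all row for other immune-related events, that action is attached to "Grade 4 or recurrent grade 3".

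For the entries that leave a choice, the first table note says: "Suspension or permanent withdrawal will be decided after discussion between the investigator and the medical supervisor". The restart note that follows is written for AK 104 that has been suspended. A further note allows resumption after grade 3-4 endocrine disorders, again where the drug was suspended. No note gives a way back after permanent withdrawal.

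**The concern.** The bullet and the table address the same decision: whether a subject who stopped AK 104 for a severe immune-related event may receive it again. The bullet answers yes for any grade 3 or 4 event, given a good response, quick resolution and a conversation with the medical monitor. The table answers by toxicity and grade, and in several rows leaves no option but to stop for good.

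What is at stake is subject safety and consistent dosing. An investigator who follows the bullet as written could re-expose a subject after, for example, grade 3 carditis or pneumonia that settled quickly on corticosteroids. An investigator who follows the table would not. Stopping and rechallenge rules belong in the protocol itself, so this is not something that a statistical analysis plan would be expected to settle.

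**Working it through.** The protocol gives no figure to reproduce. The check sets the bullet against each of the 10 rows of Table 2.

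**Row by row**

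| Table 2 row | First grade 3 event | Grade 4 event |
|---|---|---|
| Pneumonia | permanent only | permanent only |
| Diarrhea/enteritis | suspend | permanent only |
| AST/ALT, with or without bilirubin | suspend or permanent | permanent only |
| Type 1 diabetes/hyperglycemia (row has no grades) | suspend | suspend |
| Hypophysitis | suspend or permanent | suspend or permanent |
| Hyperthyroidism | suspend or permanent | suspend or permanent |
| Hypothyroidism (`cont.rem`, read as continue) | continue | continue |
| Nephritis/renal insufficiency | permanent only | permanent only |
| Carditis | permanent only | permanent only |
| All other irAEs | suspend or permanent | permanent only |

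**Counts**

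- First grade 3 event: the bullet goes beyond the table in 3 rows, is compatible in 6 and has nothing to act on in 1; 3 + 6 + 1 = 10.
- Grade 4: beyond the table in 6, compatible in 3, nothing to act on in 1; 6 + 3 + 1 = 10.
- Recurrent grade 3 in the catch-all row is also permanent only.

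Two entries need interpretation: the ungraded diabetes row and the hypothyroidism entry. Neither is among the rows in conflict, so the counts of 3 and 6 do not depend on how they are read.

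**Does anything in the protocol reconcile the two?**

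1. The bullet's own wording. It speaks of discontinuation, not suspension. Elsewhere, 1.4.1 and 8.4 add the word permanent when a final stop is meant, which suggests that the bullet has a pause in mind. But the safety part of the protocol summary uses discontinuation without qualification for adverse-event reporting. The word does not decide the matter.
2. The first table note. It gives discussion with the medical supervisor to the choice between suspending and stopping. It does not reopen rows with no such choice.
3. The restart notes. Both are confined to suspended drug.
4. The closing paragraph of 8.4 after Table 2. It deals with conflict between these principles and outside guidelines or local practice, not with conflict between the bullets and the table.

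So the protocol states no limit on the bullet and no rule of precedence.

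**Are these events real for this drug?** Section 1.1.2 reports grade 3/4 myocarditis on AK 104 monotherapy in 2 of 228 subjects: 2/228 = 0.9%, made up of 1/141 = 0.7% at 6 mg/kg and 1/50 = 2.0% at 450 mg. It also lists nephritis among the grade 3/4 related events at 10 mg/kg Q2W, in one subject: 1/18 = 5.6%. The regimens differ from the 200 mg Q3W planned here: 200/21 = 9.5 mg per day on average, against 450/14 = 32 mg per day for 450 mg Q2W. These data show only that such events occur.

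**The case against.** The best reply is that the two texts can be read together. The bullets are introduced as general recommendations, the pointer to Table 2 comes directly after them, and a specific row normally limits a general statement. The bullet is permissive, needs a good clinical course and has to pass the medical monitor. Another bullet in the same list calls for specialists, such as cardiologists, to be brought into treatment decisions. Section 1.4.1 is a risk summary, while 8.4 holds the working rules. The translation is rough, so little weight should rest on one word.

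Most of this stands, and it lowers the weight of the point. It does not remove it. The harmonised reading depends on a limit that a careful reader must supply. In 1.4.1 the bullet appears without any pointer to the table. The bullet also names grade 4, at which Table 2 lists only permanent withdrawal in every non-endocrine row.

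A reader might also infer that the infusion-reaction rules conflict. For a second grade 2 reaction at the slower rate, the 8.2 text says to stop the infusion, while Table 1 also requires withdrawal from AK 104. The documents do not support calling that a contradiction: the two statements are compatible, and 8.2 sends the reader to Table 1, which completes the instruction.

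**Conclusion.** The point holds as a gap in wording. In 8.4 and 1.4.1 the resume bullet is not limited to events for which Table 2 allows suspension. Taken literally it reaches 3 of 10 rows at a first grade 3 event and 6 of 10 at grade 4 where the table lists only permanent withdrawal, as well as recurrent grade 3 events in the catch-all row.

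Two stronger readings are tempting and not supported. One is that the protocol permits what it elsewhere forbids. Both the bullets and Table 2 are framed as recommendations, so these are two pieces of guidance that differ, not a prohibition overridden. The other is that some number of the 30 planned subjects would be re-exposed. The documents give no basis for that estimate; the row counts measure text, not frequency, and the prior events arose under other dosing.

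Severity is minor to should-fix, with moderate confidence, because a reconciling reading is available though unstated. No endpoint, analysis set or statistical figure changes.

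**What to change.** After clinical review:

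- In 8.4 and 1.4.1, limit the resume bullet to events for which Table 2 allows suspension, and add that AK 104 is not resumed after an event that the table marks only for permanent withdrawal.
- Make the next bullet, which leaves suspension or permanent termination for abnormal laboratory findings to clinical judgment, subject to the grade 4 AST/ALT row. Otherwise that row stays open by another route.
- Do not add a general clause that the tables govern unless the restart note under Table 2 is corrected first. As written, its 12-week condition makes failure to resolve a condition for restarting. Giving it precedence would undercut the clear rule in 8.4 that a subject who cannot return to AK 104 within 12 weeks stops permanently, with its stated exception for unrelated events.

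Aligning the 8.2 sentence on a second grade 2 infusion reaction with Table 1 is optional tidying.

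The cost is a wording amendment to two bullets, each of which appears in both 8.4 and 1.4.1. It adds no procedures, visits or subjects.

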**Table 2: The recommended principles for dose adjustment and toxicity management of AK 104 immune-related AEs**

Immune-related AEs	Toxicity level	Measures taken against AK 104	Management of irAE (corticosteroids and other treatments)	Monitoring and follow-up

pneumonia	Level 2	Suspension of medication	Corticosteroid hormone (initial dose of 1-2mg / kg prednisone or equivalent), then tapered thereafter	The subject was monitored for the symptoms and signs of pneumonia. Subjects with suspected pneumonia by imaging evaluation and were started on corticosteroid hormone therapy. Prophylactic use of antibiotics to prevent opportunistic infections
	Grade 3 – 4, or recurrent grade 2	Permanent withdrawal of drugs		
Diarrhea / enteritis	Level 2-3	Suspension of medication	Corticosteroid hormone (initial dose of 1-2mg / kg prednisone or equivalent), then tapered thereafter	Participants were monitored for symptoms and signs of gastroenteritis (diarrhea, abdominal pain, hematology, blood, stool, with or without fever) or bowel perforation (peritoneal irritation or intestinal obstruction). Subjects with grade 2 diarrhea and suspected enteritis should consider consulting a gastroenterologist for endoscopy to exclude enteritis
	Level 4	Permanent withdrawal of drugs		
AST/ALT	Level 2	Suspension of	Corticosteroid (initial	Monitor liver

Elevated or with an elevated bilirubin		medication	dose 0.5-1mg / kg prednisone or equivalent), tapered	function (weekly or more frequently until liver enzymes return to baseline or remain stable)
	Level 3	Suspend or permanently	Corticosteroid hormone (initial dose of 1-2mg / kg prednisone or equivalent), then tapered thereafter	
	Level 4	Permanent withdrawal of drugs	Corticosteroid hormone (initial dose of 1-2mg / kg prednisone or equivalent), then tapered thereafter	
Type 1 diabetes mellitus (T1DM) or hyperglycemia	New T1DM or hyperglycemia (related to cell failure)	Suspension of medication	T1DM subjects were started on insulin replacement therapy and hyperglycemic subjects were started on antidiabetic agents	The subject was monitored for blood glucose, or other symptoms and signs of diabetes
hypophysitis	Level 2	Suspension of medication	Use of corticosteroid hormones and, if clinically indicated, initiate hormone replacement therapy	Monitor for symptoms and signs of hypophysitis (including pituitary and adrenal dysfunction)
	Level 3-4	Suspend or permanently		
hyperthyreia	Level 2	cont.rem	Treatment with nonselective receptor blockers (e. g. propranolol) or thioamide (if appropriate)	Monitor for the symptoms and signs of thyroid disease
	Level 3-4	Suspend or permanently		
hypothyreia	Level 2-4	cont.rem	Thyroid hormone replacement therapy was initiated based on standard therapy (e. g. L Thyroxine or triiodothyronine)	Monitor for the symptoms and signs of thyroid disease

Nephritis and renal insufficiency	Level 2	Suspension of medication	Corticosteroid hormone (initial dose of 1-2mg / kg prednisone or equivalent), then tapered thereafter	Monitor for changes in renal function
	Level 3-4	Permanent withdrawal of drugs		
carditis	Level 1	Suspension of medication	Corticosteroid hormones were used based on the type and severity of the AE	Ensure adequate evaluation to confirm the cause and or to exclude other causes
	Level 2	Suspend or permanently		
	Level 3-4	Permanent withdrawal of drugs		
All of the other irAEs	Level 2, that could not be tolerated or persisted	Suspension of medication	Corticosteroid hormones were used based on the type and severity of the AE	Ensure adequate evaluation to confirm the cause and or to exclude other causes
	Level 3	AEs based on type of AE suspension or permanent withdrawal include but are not limited to Guillain-Barre syndrome, encephalitis, etc		
	Grade 4 or recurrent grade 3	Permanent withdrawal of drugs		
1. Suspension or permanent withdrawal will be decided after discussion between the investigator and the medical supervisor pay attention to:				

When the AE returns to grade 0-1 or baseline, corticosteroid hormones began to be gradually reduced for more than 4 weeks;

For AK 104 suspension: restart AK 104 if the AE returns to Grade 0-1 or baseline with corticosteroid tapering (10mg prednisone or equivalent dose) and if the AE does not resolve within 12 weeks after the last dose or 12 weeks;

For severe and life-threatening irAEs, intravenous corticosteroids and sequential oral hormone therapy should be started, and if corticosteroids are not effective, other immunosuppressants should be considered;

For subjects with grade 3-4 immune-related endocrine disorders requiring AK 104 suspension, allow medication to resume when the AE returns to level 2 and is controlled by hormone replacement therapy or achieves metabolic stability (e. g., T1DM).

Where the above principles are inconsistent with the toxicity management guidelines related to other immune checkpoint inhibitors or the local standard clinical practice, the investigator organizes the meeting to discuss the corresponding toxicity management.

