- 11) There was a past history of myocarditis, cardiomyopathy, and malignant arrhythmia. Unstable angina, congestive heart failure, or vascular disease (such as aortic aneurysm or peripheral venous thrombosis requiring surgical repair) within 2 months before the first dose, Or other cardiac lesions that may affect the safety evaluation of the study drug (e. g. poorly controlled arrhythmias, Myocardial infarction or ischemia); presence of esophageal-gastric varices within 6 months before the first dose, Severe ulcer, The wound has not healed, gastric-intestinal perforation, abdominal pain, Gastrointestinal obstruction, History of intra-abdominal abscess or acute gastrointestinal bleeding; any arterial thromboembolic event within 6 months prior to the first dose, NC I CTCAE 5.0 grade 3 and above, Transient cerebral ischemic attack, cerebrovascular accident, Hypertensive crisis or hypertensive encephalopathy; acute exacerbation of chronic obstructive pulmonary disease within 1 month before the first dose; current presence of hypertension with SBP> 160mmHg or DBP <100mmHg after oral antihypertensive medication.
- 12) History of severe bleeding tendency or coagulationopathy; blood symptoms of significant clinical significance within 1 month before the first dose, including but not limited to gastrointestinal bleeding, hemoptysis, screening imaging showing tumor wrapping around important blood vessels or significant necrosis and emptiness, and the investigator believes that participation in the study may

cause bleeding risk;

13) No response of prior anti-tumor therapy, defined as not returning to Grade 0 of NC 1 CTCAE 5.0 or 1, or the level specified in the inclusion / exclusion criteria, except for sequelae of alopecia, neurotoxicity associated with prior lead therapy. Subjects with irreversible toxicity not expected to worsen after study drug administration (e. g. hearing loss) may be included in the study after consultation with the medical monitor. Long-term toxicity from radiotherapy, subjects not recoverable as judged by the investigator may be included in the study after consultation with the medical monitor.

14) Live vaccination was administered within 30 days before the first dose, or was planned to be administered during the study period.

15) Known allergy to any component of any study drug; known history of severe hypersensitivity to other monoclonal antibodies.

16) Known history of mental illness, substance abuse, alcohol abuse, or drug use.

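### Table 2 suspends AK 104 for carditis at level 1, but the general restart note lets dosing resume at grade 1 and makes no exception for carditis

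*Protocol*

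**What the plan says.** All references are to the Protocol.

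- **Carditis row, Section 8.4, Table 2.** At the lowest level the entry reads "carditis Level 1 Suspension of medication". At the next it reads "Level 2 Suspend or permanently", and the table's footnote adds "Suspension or permanent withdrawal will be decided after discussion between the investigator and the medical supervisor". Levels 3-4 mean permanent withdrawal.
- **Restart note under Table 2.** For any AK 104 suspension the instruction is "restart AK 104 if the AE returns to Grade 0-1 or baseline with corticosteroid tapering", with 10 mg prednisone or equivalent given as the steroid level. The note does not mention carditis.
- **Endocrine note under Table 2.** Grade 3-4 immune-related endocrine disorders that needed suspension may resume at level 2, provided hormone replacement controls them or they are metabolically stable. This is the only event-specific change to the restart rule.
- **Section 8.4, general text.** "The maximum interval allowing an AK 104 pause is 12 weeks". It also says "Doctors in other fields (such as cardiology or autoimmune diseases) should be arranged to make appropriate treatment decisions" and refers sites to an oncology society guideline on checkpoint-inhibitor toxicity.
- **Text after Table 2.** Where these principles differ from other guidelines or local practice, "the investigator organizes the meeting to discuss the corresponding toxicity management".
- **Section 4.3, exclusion criterion 11.** It lists "There was a past history of myocarditis, cardiomyopathy, and malignant arrhythmia".

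**The concern.** The table treats carditis as serious enough to stop the drug at its mildest grade. That caution is not carried through to restart. The restart note was written for events that suspend at grade 2 or above, where returning to grade 0-1 means leaving the suspending range. For carditis it does not mean that, because level 1 is both a grade at which the row stops dosing and a grade at which the note allows it again.

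Two kinds of subject are affected. One has level 2 carditis, is suspended rather than withdrawn, and settles at level 1 on tapered steroids. The other has carditis that never exceeded level 1 and must be suspended, but cannot sensibly be said to return to grade 1.

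What is at stake is re-exposure to a PD-1/CTLA-4 antibody while carditis is unresolved, decided case by case with no stated grade. It is a matter of patient safety and does not touch the efficacy analysis.

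**Working it through.** The plan states no figure to reproduce. The check is a comparison of grades, followed by a rough size.

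**Step 1. Lowest suspending grade by row, against the top of the restart band (grade 1).**

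| Table 2 row | Lowest grade at which AK 104 is suspended | Above grade 1? |
|---|---|---|
| Pneumonia | 2 | yes |
| Diarrhea/enteritis | 2 | yes |
| AST/ALT | 2 | yes |
| Hypophysitis | 2 | yes |
| Hyperthyroidism | 3 (continues at 2) | yes |
| Nephritis | 2 | yes |
| All other irAEs | 2, if not tolerated or persistent | yes |
| Carditis | 1 | **no** |

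The type 1 diabetes/hyperglycemia row is ungraded, and hypothyroidism never suspends. Under the general restart note, carditis is the only row in which a suspending grade falls inside the restart band.

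**Step 2. Effect of the endocrine note.** Hypophysitis suspends at level 2, yet a grade 3-4 case may resume at level 2. The suspending and restart grades therefore also meet in that row. There the overlap is written out and made conditional. In carditis it arises by default.

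**Step 3. The carditis cases.**
- *Level 2, suspended, improved to level 1 with steroids tapered to 10 mg prednisone or equivalent.* The restart note is met, and the carditis row lists the current grade for suspension. The alternative of returning to baseline does not help, because past myocarditis is excluded at entry and a baseline of level 1 is not expected.
- *Never above level 1.* Read strictly, the event has not returned to anything, so no restart point is given. Read by grade alone, the grade condition is met on the day the drug is stopped, and the stop means little.
- *Level 3-4.* Outside this point: the row withdraws permanently and the note covers suspension only. A separate general bullet in Section 8.4 on resuming after grade 3 or 4 events raises a different question and is not used here.

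**Step 4. Size.** Inputs are the myocarditis row of the safety table in Section 1.1.2 (AK 104 alone, N=228) and the planned 30 subjects.
- Below grade 3: 3 − 2 = 1 of 228 (0.44%). By column: 6 mg/kg, 2 − 1 = 1 of 141; 450 mg, 1 − 1 = 0 of 50; 10 mg/kg, 0 of 18. Whether the one case was grade 1 or 2 is not given.
- Expected in 30 subjects: 30/228 = 0.13.
- Chance of at least one: 1 − (227/228)^30 = 0.124.
- Clopper-Pearson 95% interval for 1/228: 0.000111 to 0.0242. This gives 1 − (1 − 0.000111)^30 = 0.003 and 1 − (1 − 0.0242)^30 = 0.520.
- Redosing at level 1 after level 2 is only part of this. If an assumed share f of such events reaches that state, the chance is 1 − (1 − f/228)^30: 6.4% for f = 0.5, 3.2% for f = 0.25, 1.3% for f = 0.1. The documents give no value for f; these are illustrations.

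**The case against.** The strongest reply is that the row and the note do different jobs. The row says what to do when the event appears; the note says when a suspended subject may resume. Stopping and restart thresholds need not match, and the endocrine note shows that this table sometimes sets them apart on purpose. On that reading there is no formal contradiction. This much stands: the documents allow it. But Table 2 does not state it, and it leaves the level 1 carditis stop nearly empty, since a level 1 event already sits in the restart band.

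A second reply is that safeguards cover the decision. Table 2 is headed as recommended principles, level 2 carditis goes to joint discussion, cardiology is named among the specialists, an outside guideline is cited, and a meeting is foreseen. These do lower the risk. However, the footnote concerns suspension versus withdrawal, and the meeting is triggered by differences from other guidelines or local practice. Neither sets a restart grade. The guideline may set one; its text is not available here, so the gap is shown for the protocol text only.

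A third reply is that the restart sentence is damaged. Its 12-week clause is garbled, and nothing here rests on it; the limit is taken from the general text of Section 8.4. The grade band and the carditis grades are legible.

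Two stronger readings should be resisted. A reader might infer that carditis is the only row where restart can occur at a suspending grade; the endocrine note applied to hypophysitis shows otherwise. A reader might also infer that the protocol orders redosing at level 1; it permits it, subject to clinical judgement.

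**Conclusion.** The point holds as a minor gap in a safety rule. Carditis is the only graded row that suspends at level 1 and the only one where the overlap with the restart band arises by default, without a stated exception or condition. No carditis restart grade appears in the protocol text.

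The size is small and poorly known. At the observed rate, the chance of any below-grade-3 case in 30 subjects is about 12%, which at that rate is a ceiling for either affected state. The figure rests on a single event, and the interval runs from 0.3% to 52%. It assumes that the monotherapy rate carries over to 200 mg every three weeks with platinum, and that the myocarditis row stands for carditis as a whole. The argument for acting is the consequence of redosing with unresolved carditis and the low cost of the change, not the frequency.

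**What to change.** Add one sentence to the notes under Table 2, for example: *The grade 0-1 restart rule does not apply to carditis; after carditis of level 1 or 2, AK 104 may restart only after resolution to grade 0, with steroids tapered to 10 mg prednisone or equivalent and with the agreement of the medical monitor, within the 12-week limit; otherwise AK 104 is permanently withdrawn.*

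Grade 0 is a clinical choice that the investigators should confirm. It is the only grade that the carditis row does not list for suspension or withdrawal, and it also gives carditis that stayed at level 1 a defined restart point. If the investigators do intend restart at level 1, the notes should say so for carditis and state the conditions, as they already do for endocrine events.

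The cost is one sentence and a notice to the site. A subject whose carditis persists at level 1 may miss doses or have to stop AK 104.
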